#### 8.2.2 UC-Related Corticosteroids

[figure not shown]
The UC-related corticosteroids intercurrent event is defined as follows.

- subjects not on UC-related corticosteroids (systemic or locally acting corticosteroids for UC) at Baseline who initiated UC-related corticosteroids during the Induction Study;
- subjects on UC-related systemic corticosteroids at Baseline who have dosages increased to greater than the prednisone equivalent dose of corticosteroid taken at Baseline, or initiation of any rectal corticosteroids during the Induction Study regardless of rectal corticosteroid dose;
- subjects on UC-related rectal corticosteroids at Baseline who have dosages increased to greater than the dose taken at Baseline, or initiation of any new type of rectal or any systemic corticosteroids during the Induction Study.

The time point of the UC-related corticosteroids intercurrent event is defined as the date when one of the scenarios above occurs for a subject. As such, subjects will be considered as "non-responder" for binary endpoints at or after the occurrence of the UC-related corticosteroids intercurrent event through the end of the Induction Study. For continuous endpoints, all measurements at or after the occurrence of the UC-related corticosteroids intercurrent event through the end of the Induction Study will not be used in the analysis.

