#### 8.3.1 Categorical Endpoints

For binary efficacy endpoints, missing data will be handled using the following approaches:

[figure not shown]
• The primary approach for handling missing data in the analysis of binary endpoints will use Non-Responder Imputation while incorporating Multiple Imputation (MI) to handle missing data due to COVID-19 (NRI-C).

The NRI-C will categorize any subject who does not have an evaluation during a pre-specified visit window (either due to missing assessment or due to early withdrawal from the study) as a non-responder for the visit. The only exception is that missing data due to COVID-19 infection or logistical restrictions related to the COVID-19 pandemic will be handled by Multiple Imputation (MI). At each visit, subjects will be characterized as responders or non-responders based on MI imputed values if missing due to COVID-19; otherwise, subjects will be considered as non-responders for missing due to

other reasons in the NRI-C approach. In addition, at or after the occurrence of the UC-related corticosteroids intercurrent event (see Section 8.2.2), subjects will be counted as non-responders.

- A sensitivity analysis for categorical endpoints will use NRI with No special data handling for missing due to COVID-19 (NRI-NC).
   NRI-NC will be performed in the same way as NRI-C without the exception above. Missing due to COVID-19 infection or logistical restrictions will also be counted as non-responders. Subjects at or after the occurrence of the UC-related corticosteroids intercurrent event will still be counted as non-responders. This is the same method as the "NRI" defined in the protocol.
- Hybrid Multiple Imputation Method (HMI): Sensitivity analysis will be performed using hybrid multiple imputation method for the primary endpoint. Subjects who discontinue study drug prior to Week 8 due to lack of efficacy or AEs and have no available measurements will be considered as "non-responder" for clinical remission. Subjects who discontinue for other reasons and have no available measurements will be categorized according to the data from multiple imputations.

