- Multiple Imputation (MI) for NRI-C and HMI: Markov Chain Monte Carlo (MCMC) will be first applied to augment data into monotonic missing pattern, where applicable, and PROC MI will be used to generate 30 datasets using the regression method. The variables to be included in the imputation model are: treatment group, stratification factors (bio-IR status (bio-IR vs. non-bio-IR), Baseline corticosteroid use (yes vs. no) and Baseline Adapted Mayo score ( $\leq 7$ vs. > 7)), Baseline measurement, and if applicable, post-baseline measurements at each visit up to the end of the analysis period. The random seed for MCMC and the random seed for PROC MI are specified in Appendix D. The imputed post-baseline measurements will be rounded to the same precision as the observed data before the determination of responder status. Subjects will be characterized as responders or non-responders based on MI imputed datasets. Using the CMH model adjusted by stratification factors (bio-IR status (bio-IR vs. non-bio-IR), Baseline corticosteroid use (yes vs. no) and Baseline Adapted Mayo score ( $\leq 7 \text{ vs.} > 7$ ), the imputed endpoints will be analyzed using each of the 30 datasets. SAS PROC MIANALYZE will be used to generate the final treatment difference between upadacitinib

treatment group and placebo group and statistical inferences of the risk difference, including hypothesis testing, and 95% CI using Rubin's rule and T-distribution. Note that measurements will be set as missing at or after the occurrence of the UC-related corticosteroids intercurrent event before applying MI. After the MI imputation, an NRI override will be implemented for missing values 1) due to reasons other than COVID-19 infection or logistic reasons, or 2) at or after the occurrence of the UC-related corticosteroids intercurrent event, that is, regardless of MI imputed values, subjects satisfying 1) or 2) will be considered as "non-responder" for binary efficacy.

 As Observed (AO): The AO analysis will not impute values for missing evaluations, and thus a subject who does not have an evaluation on a scheduled visit will be excluded from the AO analysis for that visit. AO will include all values collected in the study.

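### As written, the override in SAP 8.3.1 cancels the imputation that defines the HMI sensitivity analysis

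*SAP*

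**What the plan says.** SAP 8.4.2 makes NRI-C the primary missing-data approach for clinical remission at Week 8 and names NRI-NC and HMI as sensitivity analyses. SAP 8.3.1 then defines them.

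- **HMI bullet.** It splits discontinued subjects in two. Those described as "Subjects who discontinue study drug prior to Week 8 due to lack of efficacy or AEs and have no available measurements" are non-responders. For the rest: "Subjects who discontinue for other reasons and have no available measurements will be categorized according to the data from multiple imputations".
- **NRI-C bullet.** Values missing because of COVID-19 are imputed. Non-response is assigned to values missing for "other reasons in the NRI-C approach".
- **Shared imputation bullet.** It opens "Multiple Imputation (MI) for NRI-C and HMI: Markov Chain Monte Carlo (MCMC) will be first applied" and gives the general rule "Subjects will be characterized as responders or non-responders based on MI imputed datasets". It then adds: "After the MI imputation, an NRI override will be implemented for missing values 1) due to reasons other than COVID-19 infection or logistic reasons". A second condition covers values from the corticosteroid intercurrent event onward. The effect is stated without exception: "regardless of MI imputed values, subjects satisfying 1) or 2) will be considered as" non-responders.

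Condition 2) is not in dispute. SAP 8.2.2 already imposes non-response "for binary endpoints at or after the occurrence of the UC-related corticosteroids intercurrent event through the end of the Induction Study", and Appendix E repeats this for the primary and categorical key secondary estimands.

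**The concern.** Take a subject who stops for a reason other than lack of efficacy or an adverse event, has no Week 8 data, and whose data are missing for a non-COVID reason. The HMI bullet takes this subject's status from the imputations. Condition 1) of the shared bullet makes the subject a non-responder. No sentence limits condition 1) to NRI-C or says which rule prevails, so a programmer who applies the override to both methods is following the SAP.

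What is at stake is the only planned analysis that relaxes non-responder imputation for non-COVID dropout while keeping all of ITT1 and the corticosteroid strategy. NRI-NC keeps non-response for every missing value. The analysis that excludes subjects with deviations uses NRI-C (SAP 8.4.4). The as-observed analysis drops subjects without data and, under Appendix E, uses data after the corticosteroid event. If HMI is overridden, its agreement with NRI-C would look like robustness to the dropout assumption without testing it.

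**Working it through.** **Plan's own figure.** SAP 2.4 states power above 95% for 18% versus 5% with 308 and 154 subjects, using a two-sided Fisher's exact test at 0.05. Exact enumeration gives 98.9%, so it reproduces. The present point does not depend on it.

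**Step 1: apply the rules to each kind of missing Week 8 value** (no corticosteroid event; NR = non-responder, MI = status from imputation).

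| Missing Week 8 value | NRI-C | HMI by its own bullet and the general MI rule | HMI with the override as written |
|---|---|---|---|
| Non-COVID, stopped for other reason | NR | MI | NR |
| Non-COVID, stopped for lack of efficacy or AE | NR | NR | NR |
| Non-COVID, did not stop | NR | MI | NR |
| COVID, stopped for lack of efficacy or AE | MI | NR | NR |
| COVID, other reason or did not stop | MI | MI | MI |

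The first row is the contradiction. Comparing the NRI-C column with the last column, overridden HMI differs only in the fourth row, where it moves subjects from MI to NR. Apart from random variation (Appendix D gives the two methods different seeds), it can therefore only equal or fall below NRI-C in each arm. That is the opposite of a relaxation.

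**Step 2: size of what is lost.** Inputs from SAP 2.4: 18% and 5%, with 308 and 154 subjects. The documents give no missingness rate, so I assume a share m of each arm in the first row, and a ratio r of the dropouts' remission rate to the observed rate.

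*If 18% and 5% are NRI-C rates p*, the observed rate is p/(1−m), and HMI = p + m·r·p/(1−m). The NRI-C difference is 13.0 points.

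| m | r | Upadacitinib % | Placebo % | Difference | Shift |
|---|---|---|---|---|---|
| 3% | 1 | 18.557 | 5.155 | 13.40 | +0.40 |
| 3% | 0.5 | 18.278 | 5.077 | 13.20 | +0.20 |
| 5% | 1 | 18.947 | 5.263 | 13.68 | +0.68 |
| 5% | 0.5 | 18.474 | 5.132 | 13.34 | +0.34 |

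In subjects, at r = 1 and m = 3%: 308 × 0.00557 = 1.7 extra expected remitters on upadacitinib and 154 × 0.00155 = 0.2 on placebo. At m = 5%: 2.9 and 0.4.

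*If 18% and 5% are rates among observed subjects*, NRI-C gives 13.0 × (1−m).
- 3%: 12.61, against HMI of 13.00 (r = 1) or 12.81 (r = 0.5). Shifts: +0.39 and +0.20.
- 5%: 12.35, against 13.00 or 12.68. Shifts: +0.65 and +0.33.
- 10%: 11.70, against 13.00 at r = 1. Shift: +1.30.

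The direction is not fixed if dropout is unequal. With 2% on upadacitinib and 10% on placebo, r = 1, NRI-C gives 18 × 0.98 − 5 × 0.90 = 13.14, above the 13.00 from HMI.

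Under the override the first-row subjects contribute no remitters in any of these cases.

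**Step 3: yardstick.** SE = √(0.18 × 0.82/308 + 0.05 × 0.95/154) = 2.81 points. The 95% half-width is 1.96 × 2.81 = 5.50 points.

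**The case against.** The best reply is that the documents point to the intended reading. The NRI-C bullet attaches the rule in condition 1) to NRI-C by name, and HMI has its own rule for other-reason discontinuation, which would have almost no effect if overridden. A specific definition normally governs a paragraph on shared mechanics. I agree that this is probably what was meant. But the SAP states no precedence, and the override is equally explicit: it comes later, in the operational paragraph whose title names HMI, and applies whatever was imputed. The version 3.0 entry in the version history, on multiple imputation for data missing because of COVID-19 and other reasons, does not settle it; it could describe either reading.

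A second reply is that few subjects are affected. Protocol 5.4.1 asks subjects who stop study drug to keep attending visits, and SAP 8.2.1 uses their data. That stands, and it limits the size.

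A third is that the HMI bullet does not mention non-COVID missing values in subjects who did not stop treatment, so a repair that imputes them goes beyond the contradiction. The bullet is indeed silent on them. Once condition 1) is confined to NRI-C, however, the shared bullet's general rule already takes their status from the imputed datasets. The repair should say so openly.

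**Conclusion.** The contradiction is real, and applied as written it turns HMI into a near-copy of the primary analysis. Under the equal-dropout assumptions of 3% to 5% per arm, the forgone change is 0.20 to 0.68 points on a 13.0-point difference; even 10% gives about 1.3 points, well inside the 5.5-point half-width. These figures rest on assumed missingness and remission ratios, since the documents give neither. The primary NRI-C analysis, NRI-NC, the fixed testing sequence and the sample size are untouched. The loss is a sensitivity analysis that does not test the assumption it was included to test, so the text should be corrected although the primary result is not threatened.

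**What to change.** In the shared imputation bullet of SAP 8.3.1, confine override condition 1) to NRI-C and keep condition 2) for both methods. Add a sentence to this effect: under HMI, non-response is imposed only on (a) subjects without measurements who stopped study drug before Week 8 for lack of efficacy or an adverse event, and (b) values from the corticosteroid event onward; every other missing value keeps its imputed status. The last clause also settles missing values in subjects who did not stop treatment.

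The cost is one limiting clause and one sentence. HMI seeds already exist in Table D-2, and no new data are needed. Protocol 8.1 plans to finalize the SAP before database lock, and SAP 2.3 places unblinding for analysis with lock, but the documents do not show whether unblinding preceded version 6.0. If the data are already unblinded, the study report should state which rule was programmed for HMI.

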#### 8.3.2 Continuous Endpoints

For continuous endpoints, missing data will be handled using Mixed-Effect Model Repeat Measurement (MMRM).

The MMRM will be conducted using mixed model including observed measurements at all visits, except that measurements at or after the occurrence of UC-related corticosteroids intercurrent event will be excluded (see Section 8.2.2). The mixed model includes the categorical fixed effects of treatment, visit and treatment-by-visit interaction, randomization stratification factors (bio-IR status [bio-IR vs. non-bio-IR], Baseline corticosteroid use [yes vs. no] and Baseline Adapted Mayo score [≤ 7 vs. > 7]), and the continuous fixed covariates of Baseline measurements. An unstructured variance covariance matrix (UN) will be used. If the model cannot converge, an autoregressive (1) or compound symmetric (CS) covariance structure matrix will be used. The parameter estimations are based on the method of restrictive maximum likelihood (REML). The fixed effects will be used to report model-based means at corresponding visits.

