5.5.3 Method of Assigning Subjects to Treatment Groups

All subjects will be centrally randomized using a web based Interactive Response Technology (IRT).

All subjects will be assigned a unique identification number by the IRT at the Screening Visit. In Part 1, 462 subjects who meet all the inclusion and none of the exclusion criteria defined in Section 5.2.1 and Section 5.2.2 will be centrally randomized in a 2:1 ratio to receive one of two treatment groups at Baseline (Week 0) in a double-blind manner (upadacitinib 45 mg QD, or placebo QD). The randomization will be stratified by bio-IR status (bio-IR vs non-bio-IR), corticosteroid use (yes or no) and Adapted Mayo score (≤ 7 or > 7) at Baseline. Within bio-IR, the randomization will be further stratified by number of prior biologic treatments (≤ 1 or > 1). Within non-bio-IR, the randomization will be further stratified by previous biologic use (yes or no).

The IRT will assign a randomization number that will encode the subject's treatment group assignment according to the randomization schedule generated by the Statistics Department at AbbVie and as per Section 5.1 definitions.

IRT will provide the appropriate medication kit number(s) to dispense to each subject as per Section 5.1. Study drug will be administered at the study visits as summarized in Section 5.1. Returned study medication should not be re-dispensed to any subject.

All subjects will keep the same unique subject identification number throughout the study and program.

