8.1.6.2 Secondary Efficacy Variables

All secondary efficacy variables are listed in Section [5.3.3.2](#).

In general, continuous secondary efficacy variables with repeated measurements will be analyzed using a Mixed Effect Repeated Measure (MMRM) model. Continuous secondary efficacy variables which are collected at only one post-baseline visit (such as Mayo score) will be analyzed using an Analysis of Covariance (ANCOVA) model. Categorical secondary efficacy variables will be analyzed using the CMH test controlling

for stratification variables. NRI for missing data will be used for categorical secondary endpoints. The ranked secondary analysis will be repeated in the ITT2 population.

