#### 2.3 Treatment Assignment and Blinding

In Part 1, approximately 462 subjects will be randomized in a 2:1 ratio to DB upadacitinib 45 mg QD or matching placebo for 8 weeks. The randomization will be stratified by bio-IR status (bio-IR vs. non-bio-IR), corticosteroid use (yes vs. no) and Adapted Mayo score ( $\leq 7 \text{ vs.} > 7$ ) at Baseline. Within bio-IR, the randomization will be further stratified by number of prior biologic treatments ( $\leq 1 \text{ vs.} > 1$ ). Within non-bio-IR, the randomization will be further stratified by previous biologic use (yes vs. no).

All eligible subjects entering Part 2 will receive OL upadacitinib 45 mg QD for an additional 8 weeks (until Week 16).

The primary analysis will be performed after all ongoing subjects have completed the study activities and the database has been locked. Treatment assignments will be unblinded to AbbVie for statistical analyses. The study sites and subjects will remain blinded to the DB induction treatment assignments until all subjects have completed the Maintenance Study.

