## 3.2 Secondary Endpoints

The ranked secondary efficacy endpoints for Part 1 under overall type I error control are as follows:

[figure not shown]
- 1. The achievement of endoscopic improvement at Week 8;
- 2. The achievement of endoscopic remission at Week 8;
- 3. The achievement of clinical response per Adapted Mayo score at Week 8;
- 4. The achievement of clinical response per Partial Adapted Mayo score at Week 2;
- 5. The achievement of histologic-endoscopic mucosal improvement at Week 8;
- 6. The achievement of no bowel urgency at Week 8;
- 7. The achievement of no abdominal pain at Week 8;
- 8. The achievement of histologic improvement at Week 8;
- 9. Change from Baseline in IBDQ total score at Week 8;
- 10. The achievement of mucosal healing at Week 8;
- 11. Change from Baseline in FACIT-F score at Week 8.

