#### 8.5.1 Key Secondary Efficacy Analyses

The key secondary endpoints are defined in Section 3.2. The estimands corresponding to the secondary efficacy endpoints are defined in Section 2.1. Details of the estimand definitions are outlined in Appendix E. For ITT1 Population, secondary efficacy endpoints in Part 1 will be analyzed by comparing upadacitinib treatment group and placebo group. The binary secondary endpoints will be analyzed by CMH and the corresponding analyses are specified in Section 8.3.1. The NRI-C will be the primary approach for missing data handling in the analyses of binary secondary efficacy endpoints. The NRI-NC approach will be used as sensitivity analyses.

The continuous secondary endpoints will be analyzed by MMRM and the corresponding analyses are specified in Section 8.3.2.

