## 12.0 Overall Type-I Error Control

The overall type I error rate of the primary and the ranked secondary endpoints will be strongly controlled using the fixed-sequence multiple testing procedure. Specifically, the testing will utilize the endpoint sequence of the primary and ranked secondary endpoints in the order as specified in Section 3.1 and Section 3.2 at the  $\alpha$  level of 0.05 (two-sided).

No multiplicity adjustment will be applied to the additional efficacy endpoints listed in Section 3.3. The analysis for additional efficacy endpoints will be performed at the nominal  $\alpha$  level of 0.05 (two-sided).

[figure not shown]
Since there are no efficacy analyses for early stopping planned for the DMC review, no  $\alpha$  spending is needed due to the DMC review.

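### The MMRM for IBDQ and FACIT-F omits the nested prior-biologic randomization factor, at a small possible cost in precision

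*SAP*

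**What the plan says.** SAP 2.3 and Protocol 5.5.1 and 5.5.3 stratify randomization by bio-IR status, corticosteroid use and Adapted Mayo score (7 or below versus above 7), and then go one level deeper. In the protocol's words, "Within bio-IR, the randomization will be further stratified by number of prior biologic treatments" (at most one versus more than one). In the SAP's, "Within non-bio-IR, the randomization will be further stratified by previous biologic use (yes vs. no").

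SAP 8.3.2 describes the MMRM terms as treatment, visit, their interaction, the baseline measurement, and the "randomization stratification factors (bio-IR status [bio-IR vs. non-bio-IR], Baseline corticosteroid use [yes vs. no" together with Adapted Mayo score. The list ends there. SAP 8.5.1 sends the ranked continuous endpoints to this model: "The continuous secondary endpoints will be analyzed by MMRM and the corresponding analyses are specified in Section 8.3.2". These are rank 9, "Change from Baseline in IBDQ total score at Week 8", and rank 11, the FACIT-F change at Week 8. SAP 12.0 states that type I error over the primary and ranked endpoints is "strongly controlled using the fixed-sequence multiple testing procedure".

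The protocol fixes the type of model but no covariate list: "In general, continuous secondary efficacy variables with repeated measurements will be analyzed using a Mixed Effect Repeated Measure (MMRM) model". Neither document explains why the nested factor is dropped, and the SAP version history in Section 13.0 does not mention it.

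**The concern.** A model that claims to adjust for the randomization factors should list all of them or say which are pooled. SAP 8.3.2 does neither, so a reader of that section alone would think that the model matches the randomization.

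Stratified randomization balances the arms on the nested factor. If that factor is prognostic and is left out, its variation between levels goes into the residual. The reported standard error then overstates the real uncertainty of the treatment difference, and the confidence interval and test are slightly conservative. The endpoints at stake are IBDQ and FACIT-F. Because the testing sequence is fixed, the IBDQ result also decides whether ranks 10 and 11 are formally tested.

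**Working it through.** **The plan's own figure.** The documents give no power or precision figure for IBDQ or FACIT-F. The one sample-size figure, more than 95% power for the primary endpoint (154 versus 308 subjects, 5% versus 18%, two-sided Fisher's exact test at 0.05), reproduces: 98.8% by normal approximation and 98.9% by exact enumeration. It does not depend on the MMRM terms.

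**Inputs from the documents.**
- 2:1 allocation of about 462 subjects.
- 6 subjects at one site excluded from efficacy (SAP 4.0), so about 462 - 6 = 456. The 462 is a planned figure.
- Non-bio-IR share 25% to 50%.
- Prior biologic use in at most 20% of non-bio-IR subjects, that is, at most 0.20 × 0.25 × 462 = 23 to 0.20 × 0.50 × 462 = 46 subjects.
- IBDQ and FACIT-F at Baseline, Week 2 and Week 8 in Part 1 (Protocol synopsis).

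**Assumptions, not in the documents.**
- s = 55% bio-IR.
- p = 60% of bio-IR with more than one prior biologic.
- q = 20% of non-bio-IR with prior use (the cap).
- d, the outcome gap between nested levels in residual-SD units, beyond all terms already in the model, including the baseline measurement.

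**Closed form.** The omitted variance relative to the residual is V = [s·p(1-p) + (1-s)·q(1-q)]·d², and the standard error is inflated by r = √(1 + V).
- Equal gap in both populations: 0.55 × 0.24 + 0.45 × 0.16 = 0.132 + 0.072 = 0.204.
- No gap in non-bio-IR: 0.132 only.

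| Gap d | Non-bio-IR gap | V | r | SE excess |
|---|---|---|---|---|
| 0.2 | none | 0.00528 | 1.0026 | 0.3% |
| 0.2 | equal | 0.00816 | 1.0041 | 0.4% |
| 0.5 | none | 0.0330 | 1.0164 | 1.6% |
| 0.5 | equal | 0.0510 | 1.0252 | 2.5% |

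With q = 10% and an equal gap, V at d = 0.5 is (0.132 + 0.45 × 0.09) × 0.25 = 0.0431, and the excess is 2.1%.

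**Effect on a test.** The estimate itself is no more variable, because the arms are balanced on the factor; only the reported standard error grows. A test with 90% power when the factor is included therefore has power Φ(1.960 + 1.282 - 1.960·r) without it: 89.9% at d = 0.2, and 89.4% (no non-bio-IR gap) or 89.1% (equal gap) at d = 0.5.

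**Simulation check.** Two-visit MMRM, unstructured covariance, REML, 1,500 trials per scenario, 456 subjects, blocks of 3, true Week 8 effect 0.324 SD, equal gap in both populations. Further assumptions were a correlation of 0.6 between Week 2 and Week 8, 8% missing at Week 8, 40% on corticosteroids and 40% with Adapted Mayo above 7.

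| Gap | SE, three factors | SE, with nested factor | Ratio | Power |
|---|---|---|---|---|
| 0 | 0.1022 | 0.1022 | 0.9998 | – |
| 0.2 | 0.1026 | 0.1023 | 1.0037 | 88.1% vs 88.3% |
| 0.5 | 0.1046 | 0.1020 | 1.0246 | 87.1% vs 88.4% |

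At a gap of 0.5 the empirical SDs of the estimate were 0.1022 and 0.1020. This confirms that the reported three-factor SE is the one that is off. False-rejection rates at that gap were 3.9-4.2% with three factors and 4.5-4.6% with the nested factor (Monte Carlo SE about 0.5 points), so the error is in the conservative direction.

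**The case against.** The strongest reply is that this is a preference about covariates. The three-factor set is used throughout the plan, the bracketed list in SAP 8.3.2 leaves no programmer in doubt about the model, and the nested variables are still summarised at baseline (SAP 7.1). That is fair: the label is incomplete but does not make the model ambiguous.

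A second reply is that 2.5% sits near the top of the range. It takes prior use in non-bio-IR at its 20% cap and gives that group the same gap as multiple biologics in bio-IR. Yet those non-bio-IR subjects stopped a biologic for reasons other than failure or intolerance, and nothing in the documents suggests equal gaps. This stands, and it is why the lower figures, 0.3% and 1.6%, are shown. The factor must also predict beyond the baseline measurement, which makes a 0.5 SD gap harder to reach.

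Three stronger readings are tempting, and the documents support none of them.
- **The omission biases the comparison or inflates type I error.** It does not: the factor is balanced by randomization, and the error is conservative.
- **The SAP contradicts the protocol.** Protocol 8.1.6.2 gives no covariate list for the MMRM, and the three-factor CMH for the primary endpoint is the same in both documents.
- **The imputation model needs the same change.** SAP 8.3.1 does have the same gap: "The variables to be included in the imputation model are: treatment group, stratification factors", followed by the same three. But that model supplies the imputed datasets for NRI-C, the primary missing-data approach for the primary endpoint (SAP 8.4.2), so changing it would alter the primary analysis. In simulation (1,500 trials, 30 imputations each), bias in the risk difference with three factors was 0.04 percentage points or less in three of four scenarios. It reached 0.15 points (versus 0.01 with the nested factor) only with a 0.5 SD gap and COVID-19 missingness of 15% versus 5% across nested levels. That gain does not justify touching the primary analysis.

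**Conclusion.** The point holds as a minor improvement. The MMRM for ranked endpoints 9 and 11 leaves out one randomization factor without explanation and labels the other three as if they were the full set. The cost is a standard error that is too large by about 0.3-0.4% at a 0.2 SD gap and 1.6-2.5% at a 0.5 SD gap, given 55% bio-IR with 60% of them on more than one prior biologic. The lower ends assume no gap in non-bio-IR, the upper ends an equal gap with 20% prior use. With no gap the loss is essentially zero. The omission is certain from the text; the size of the benefit is not, because the documents give no gaps, SDs or prevalences. Because IBDQ comes before ranks 10 and 11, the small gain in power is worth having, but it is unlikely to decide the sequence.

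**What to change.** In SAP 8.3.2 only, replace the two-level bio-IR term in the MMRM by one four-level factor:
- bio-IR with at most one prior biologic
- bio-IR with more than one
- non-bio-IR with previous biologic use
- non-bio-IR without

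Keep corticosteroid use, Adapted Mayo score and all other terms. Correct the label so that it matches SAP 2.3, and record the change in Section 13.0 before unblinding. SAP version 6.0 does not say whether treatment codes are open. If they are, keep the three-factor MMRM for the ranked tests, correct the label, and run the extended model as a sensitivity analysis.

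Leave the three-factor CMH and the imputation model in 8.3.1 unchanged.

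The cost is two extra parameters and one version entry. The factor is already collected for randomization. With no nested effect the SE ratio was 0.9998, so practically nothing is lost. The factor enters as main effects, so the small non-bio-IR group with prior use creates no sparse strata; sizes well below its cap were not simulated. The one drawback is that continuous and binary ranked endpoints would then use slightly different adjustment sets, which the SAP should state.
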